## 10.0 Data Handling and Statistical Considerations

---

- 10.1 **Sample Size and Statistical Power:** Allowing for 30% of participants who may not provide complete data (as in our prior study), we will need to enroll a total of 720 participants to have 504 fully evaluable participants (168 evaluable in each of the three study arms). Fully evaluable participants is defined as having completed the On Study/ Participant Interview and the Clinical Record Information (baseline), the ISI, PSQI, Daily Diaries, and actigraphy (baseline and post-intervention assessments) for primary and secondary endpoints. With 504 fully evaluable participants, will have 80% power at a 0.025 significance level to test our hypotheses. We will use a significance level of 0.025 to control for type I error because two hypotheses (i.e., 1 inferiority [yoga vs. CBT-I] and 1 superiority [yoga vs. health education]) will be tested in our primary aim. *[Note: We will reimburse survivors for participating in this study in an effort to decrease attrition and data loss.]*
- 10.2 **Power for Primary Aim 1:** The two primary hypotheses to be tested in our primary aim include: (1) YOCAS® will be as effective as CBT-I, and (2) YOCAS® will be more effective than the health education control.
- 10.2.1 **Power for Hypothesis 1:** Based on baseline data from our previous phase III RCT examining the effects of yoga on insomnia and data from Savard and Morin, we assume an ISI standard deviation of 4.6. Since half a standard deviation is commonly accepted as appropriate for estimating a clinically important change, we regard a difference of 2.3 (half a standard deviation) between YOCAS® and CBT-I as nontrivial. Following the same methods as Garland and colleagues, we set the non-inferiority margin to 1.15 (half of the 2.3 difference). We will test the **null** hypothesis that the difference in mean change on the ISI between YOCAS® and CBT-I is greater than 1.15; that is, YOCAS® is *inferior* to CBT-I. Rejection of the null hypothesis means that YOCAS® is as effective (*non-inferior*) as CBT-I. Using ANCOVA to estimate differences in mean change between YOCAS® and CBT-I, a correlation of 0.576 (from our prior study), and a sample of 168 subjects per group, we will have sufficient (80%) power to detect non-inferiority using a margin of 1.15 at  $p = 0.025$ .

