- 10.2.2 **Power for Hypothesis 2:** Using ANCOVA to estimate differences in mean change between YOCAS® and health education, a correlation of 0.576 (from our prior study), and a sample size of 168 evaluable subjects per group, we will have sufficient power to detect differences on the ISI of at least 1.3, 1.5 and 1.6 (all larger than our 1.15 non-inferiority margin) at 80%, 90%, and 95% power, respectively. (Note: It is already well-established that CBT-I is superior to general health education and equal time and attention, as such an overall test of group differences is not necessary or sufficient—the differences in question are specifically between yoga and CBT-I and yoga and health education and require two separate hypotheses be tested.)
- 10.3 **Study Timeline:** Based on our prior experience conducting studies in the URCC Research Base, we anticipate that study start-up activities (e.g., obtaining NCI and IRB approvals, presenting the protocol and training NCORP site staff, setting up databases, registration and randomization, ordering supplies and making kits and manuals, sending kits and other study supplies to NCORPs) will take approximately 6 months. Screening and accruals will

begin during the 7th month and continue through month 54. The final 6 months will be used to retrieve any remaining data, supplies and equipment from NCORPs, to conduct final audits of the data, to conduct analyses, to write abstracts and papers, and to present findings at meetings. We expect it will take between 24 and 47 months to accrue the 720 participants needed for this study.

- 10.4 **Representation of Women and Minorities:** None of the eligibility criteria for the study involve gender or ethnicity. Past enrollment in our NCORP studies has closely paralleled the gender and ethnic composition of the available population. See section 12.0 on Gender and Minorities.
- 10.5 The same **protocols and procedures for data quality and control** that we have used for our previous URCC Research Base protocols will be used for this study. Data will be entered on scannable forms (Teleform) and electronically sent to a Microsoft Access database. After scanning, data are audited visually for errors, and then the entire database is re-audited. MPlus, R and SAS statistical packages will be used for the analyses.

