- 10.6 Unless otherwise stated, all statistical tests will be performed at the two-tailed 5% level of significance. Likewise, 95% confidence intervals will be constructed for estimation of effects (e.g., difference in mean CRF, aerobic capacity, strength and QOL between the active treatment group and the control group). Data will be analyzed on an "intent-to-treat" basis; participant data will be included in the treatment group to which the participant was randomized, regardless of any subsequent changes to the treatment (treatment in this study is considered the study intervention, i.e., exercise intervention, CBT-I, or Health education standard care).
- 10.6.1 **Assumptions.** The assumptions underlying all statistical analyses will be thoroughly checked using appropriate graphical and numerical methods. For the ANCOVA analyses, the assumptions are bivariate normality of the Pre- and Post-treatment responses with common covariance matrices, after correction for the model fixed effects. Bivariate normality will be assessed with Roysten's procedure, and equality of the covariance matrices will be assessed with the Box M test. The ISI data from our previous trial did not show violations of these assumptions. If distributions are markedly skewed, we will apply transformations as appropriate. The biomarker data will likely require a logarithmic transformation, as is common practice. If heteroscedistic variance is found in the residuals for any of the models, a Box-Cox transformation will be applied to the data. As a last resort, appropriate nonparametric methods will be attempted, e.g. Wilcoxon rank sum test on change scores. If outliers or influential data are detected, the accuracy of the data will be investigated. If no errors are found, analyses may be repeated after removing these cases to evaluate their impact on the results. However, the final analyses will include these data points.

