- 10.6.2 **Missing Values.** Every effort will be made to facilitate participants' completion of questionnaires and provision of actigraphy and physical function data, and blood. In the event of missing data, the reasons for missing data will be recorded and tabulated according to treatment group. Some missing data are inevitable. Under the missing at random (MAR) assumption, we will use multiple imputation to obtain unbiased estimates of key parameters. If data are suspected to be missing not at random (MNAR), a sensitivity analysis using the methods of Liublinska and Rubin (2014) will be run to determine the impact on results. If the estimates are similar to the ones obtained from the simpler analysis of only complete cases, we will report the complete-case analysis results.
- 10.7 **Statistical Analyses:**
- 10.7.1 **Primary Aim 1 Analyses:** To determine if YOCAS® is as effective as CBT-I and more effective than health education for improving **insomnia (ISI total)**, two separate analyses will be performed, each aimed at estimating the difference between arms in mean change from baseline with associated confidence intervals. The comparison of YOCAS® to CBT-I is a non-inferiority hypothesis with a one-sided alpha, and the comparison of YOCAS® to the health education control is a traditional null hypothesis of no difference with a two-sided alpha. See the Statistical Power section for more details. A linear mixed effects ANCOVA will be used to assess the statistical significance of the differences in mean changes from baseline for the two groups (Hypothesis 1 = YOCAS® vs. CBT-I;

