Hypothesis 2 = YOCAS® vs. health education). **The response will be post-treatment ISI total score.** The model fixed effects will be Group and Baseline ISI. NCORP Site will be included as a random effect. The REML method will be used to estimate the random effect variance components. If the NCORP Site variance component is significant, the fixed effects will be tested using F tests with the Kenward-Roger degrees of freedom adjustment. If the NCORP Site variance component is not statistically significant, we will use ordinary least-squares estimation and F-Tests for testing the fixed effects. The mean difference between groups with associated 95% confidence intervals will be estimated using the appropriate contrasts. An alpha level of 0.025 will be used to adjust for multiple comparisons. Additional follow-up analyses will include NCORP site and cohort as covariates and examine possible interactions.

- 10.7.2 **Secondary Aim 2 Analyses:** To examine if YOCAS® is effective for improving **objective symptoms of insomnia** (sleep latency, sleep efficiency, wake after sleep onset, sleep duration, and daytime napping via actigraphy) and **global sleep quality impairment** (PSQI total) compared to CBT-I and a health education control, we will use the same methods as for Primary Aim 1 with no multiple comparison adjustments.

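### The 0.025/0.025 split of the primary alpha is valid, but it keeps Hypothesis 2 at two-sided 0.025 even after Hypothesis 1 is met; a step-down rule would add a little power within the same 0.05 limit

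*Combined protocol and SAP*

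**What the plan says.** Section 10.1 gives the reason for the reduced level: "We will use a significance level of 0.025 to control for type I error because two hypotheses" are tested in the primary aim. Section 10.7.1 repeats the level: "An alpha level of 0.025 will be used to adjust for multiple comparisons". The same section says that the comparison with CBT-I "is a non-inferiority hypothesis with a one-sided alpha" and that the comparison with health education "is a traditional null hypothesis of no difference with a two-sided alpha". The general rule in 10.6, that "all statistical tests will be performed at the two-tailed 5% level of significance", applies only where nothing else is stated, so it does not override 10.1 and 10.7.1.

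The level also underlies the power statement for H2 in 10.2.2: "we will have sufficient power to detect differences on the ISI of at least 1.3, 1.5 and 1.6", at 80%, 90% and 95% power. No section gives a testing order, a Holm-type rule, gatekeeping, or reuse of alpha after a rejection. Section 10.7.1 plans 95% intervals for the group differences.

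**The concern.** Under a plain split, each hypothesis keeps its own 0.025 whatever the other result. Once H1 has been rejected, its 0.025 is no longer needed to protect the family and can be added to the level for H2. The plan does not do this. A result with YOCAS shown non-inferior to CBT-I and a two-sided p-value for H2 between 0.025 and 0.05 would count as a failed superiority claim, although a rule with the same familywise limit would allow it.

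This touches the trial's main purpose. Section 2.0 describes the benefit in joint terms: YOCAS at least as effective as CBT-I and also more effective than health education.

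**Working it through.** **Inputs (10.1, 10.2.1, 10.2.2).** ISI standard deviation 4.6; baseline-to-post correlation 0.576; 168 evaluable per arm; margin 1.15; H1 one-sided 0.025; H2 two-sided 0.025. Normal approximation, no clustering, as in the plan's own calculation.

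**Reproducing the plan.**
- ANCOVA standard deviation = 4.6 × √(1 − 0.576²) = 3.760.
- Standard error of a pairwise difference = 3.760 × √(2/168) = 0.4103.
- H1 power with no true difference = Φ(1.15/0.4103 − 1.960) = 80.0%, as stated.
- H2 detectable difference = (2.2414 + z_power) × 0.4103 = 1.265, 1.445 and 1.594 at 80%, 90% and 95%. Rounded up, these are the stated 1.3, 1.5 and 1.6. At two-sided 0.05 they would be 1.149, 1.330 and 1.479, so the stated figures do rest on the split level.

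**Step-down rule.** Reject H1 if Z1 > 1.960. Reject H2 if |Z2| > 2.2414, or if H1 is rejected and |Z2| > 1.960. The two statistics share the YOCAS arm with equal arm sizes, so their correlation is 0.5.

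**Familywise error.**
- Both nulls true: a first false claim needs H1 at 0.025 or H2 at 0.025, exactly as under the split. The bound is 0.05; the computed value is 0.047 for both rules.
- Only the H1 null true: at most 0.025.
- Only the H2 null true: at most 0.05, because H2 is never tested above that level. Computed: 0.042 if yoga equals CBT-I, approaching 0.050 as yoga becomes better than CBT-I.

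The bounds need no assumption about the correlation. Every rejection under the split is kept.

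**H2 power.** P(|Z2| > 2.2414) + P(Z1 > 1.960 and 1.960 < |Z2| ≤ 2.2414), with means (1.15 − w)/0.4103 for Z1 and d/0.4103 for Z2. Here w is the true shortfall of yoga against CBT-I and d is its true advantage over health education. The non-zero values of w are assumptions.

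| w | P(H1 met) | d | Split | Step-down | Gain (points) |
|---|---|---|---|---|---|
| 0 | 80.0% | 1.3 | 82.3% | 86.4% | 4.1 |
| 0 | 80.0% | 1.5 | 92.1% | 93.9% | 1.8 |
| 0 | 80.0% | 1.6 | 95.1% | 96.2% | 1.1 |
| 0.5 worse | 35.4% | 1.3 | 82.3% | 83.3% | 0.9 |
| 0.5 better | 98.0% | 1.3 | 82.3% | 88.4% | 6.1 |

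With w = 0, the overall detectable differences become 1.19, 1.38 and 1.54. The chance that both hypotheses succeed at d = 1.3 goes from 70.3% to 74.4%.

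**Dependence on how well CBT-I works.** The advantage of CBT-I over health education is A = d + w. The documents give no figure for A, so it is varied here. For each A, w is varied from 0 upward (yoga no better than CBT-I) and the largest gain in H2 power is kept.

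| A | Largest gain (points) |
|---|---|
| 1.5 | 3.0 |
| 1.8 | 0.9 |
| 2.0 | 0.3 |
| 2.3 | 0.05 |

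**The case against.** The strongest reply is that nothing is broken. A fixed split is a recognised and valid choice, it agrees with the sample-size calculation, and H2 already has its stated power. All of that stands. A reader might infer from the missing step-down rule that the primary analysis is wrong or that H2 is underpowered. The documents do not support that: the figures in 10.2 reproduce under the split.

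The second reply concerns size. The gain needs yoga close to CBT-I and, at the same time, H2 still in doubt. Section 10.2.2 treats the superiority of CBT-I over general health education as established, and 10.2.1 regards 2.3 points as a nontrivial difference. If CBT-I has an advantage of that order and yoga matches it, H2 power is already about 99.96%. If yoga is much weaker than CBT-I, H1 rarely succeeds and little alpha is passed on: with w = 1.0 and d = 1.3, H1 is met about 5.5% of the time and H2 power gains less than 0.1 point. This stands too, and it limits the point to a modest one.

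The third reply is that the split buys something, so it would be too strong to say that its strictness has no return. It holds H2's own false-positive rate at 2.5% and gives H2 one fixed interval level. Under the step-down rule that rate is 4.2% if yoga equals CBT-I and can approach 5.0%, and the matching interval depends on the H1 result. These are real costs. The first is mostly remote: if yoga is no better than health education and CBT-I is better than both by 1.15 or more, H2's error is at most 2.7%.

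None of this removes the basic comparison. For the same familywise limit, the step-down rule keeps every rejection that the split makes and adds some.

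**Conclusion.** The point holds as an inexpensive gain in efficiency, not as an error. The plan leaves H2 at two-sided 0.025 after H1 is met, and a step-down rule with the same 0.05 limit would do slightly better. If yoga equals CBT-I, the gain in H2 power is 4.1 points at a true difference of 1.3, 1.8 at 1.5 and 1.1 at 1.6. It is under 1 point at 1.3 if yoga is 0.5 or more points worse than CBT-I. If yoga is no better than CBT-I and CBT-I beats health education by 2 points or more, it is at most about 0.3 point. A claim that a true yoga benefit would often be missed under the present plan goes further than the documents allow.

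The power figures rest on the plan's standard deviation, correlation and evaluable numbers, on independent observations, and on the normal approximation. The 0.05 limit does not depend on the correlation between the two tests. It adds a one-sided 0.025 and a two-sided 0.025, as the plan itself does.

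**What to change.** Before unblinding, amend 10.1 and 10.7.1 as follows.

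- Test H1 at one-sided 0.025 in every case.
- Test H2 at two-sided 0.025, or at two-sided 0.05 if H1 has been rejected.
- Report both 95% and 97.5% intervals for H2, and state which one matches the test that applied. The 95% interval planned now does not match a two-sided 0.025 test; the 97.5% interval does.
- Restate 10.2.2 for this rule: overall detectable differences of about 1.19, 1.38 and 1.54 at 80%, 90% and 95% power, in place of 1.27, 1.45 and 1.59, with the condition that yoga equals CBT-I.

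A fixed order with H2 first is not recommended. It would make H1 conditional on H2 and lower the chance of claiming H1 from 80% to about 74% at a true H2 difference of 1.3.

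The change costs SAP wording only: no added participants, data or visits. The sponsor accepts a higher type I error for H2 alone, up to 5%, and an H2 interval level that depends on the H1 result. A sponsor that prefers the stricter H2 test can keep the split and should say so.

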- 10.7.3 **Secondary Aim 3 Analyses:** To examine if YOCAS® and CBT-I are effective for **maintaining improvements in insomnia at 3 and 6 months post-intervention** compared to a health education control, we will perform a longitudinal analysis using the ISI total score at all five time points as the response. The fixed effects will be Time, Group (all three in this analysis), and Time by Group interaction. Within-subject random effects will initially be modeled assuming an unstructured covariance matrix, but will be simplified after inspection of the estimated covariance structure (e.g., compound symmetry). If NCORP Site variance in the primary analysis is statistically significant at the 0.05 level, it will be included as an additional random effect, independent of the within-subject random effects. REML estimation will be used. Fixed effects will be tested using F tests with the Kenward-Roger degrees of freedom adjustment. The impact of group on the time trajectory of insomnia will be tested via the Time\*Group interaction. Least-squares means for each Time and Group combination will be plotted to visualize and understand the time trajectories of insomnia. Differences in time trajectories between the three groups will be tested with no adjustments for multiple comparisons.

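### The 3- and 6-month insomnia model (10.7.3) gives each arm a free baseline mean, so it omits the baseline regression adjustment used in the primary analysis; on the plan's own SD and correlation, adjusting would cut the variance of the planned contrast by about 21%

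*Combined protocol and SAP*

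**What the plan says.** Section 10.7.3 (Secondary Aim 3, durability) describes a longitudinal analysis "using the ISI total score at all five time points as the response". Its mean model is given as: "The fixed effects will be Time, Group (all three in this analysis), and Time by Group interaction". On covariance it says: "Within-subject random effects will initially be modeled assuming an unstructured covariance matrix", with later simplification allowed. "The impact of group on the time trajectory of insomnia will be tested via the" Time-by-Group interaction. Visit-specific means appear only as a display: "Least-squares means for each Time and Group combination will be plotted to visualize and understand the time trajectories of insomnia". The section mentions neither a baseline covariate nor a common baseline mean across arms.

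Section 10.7.1 (Primary Aim 1) treats the same endpoint differently. The response is post-treatment ISI, and "The model fixed effects will be Group and Baseline ISI". Aims 2 and 4 reuse the Aim 1 method (10.7.2, 10.7.4).

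For the primary power calculation, section 10.2.1 says "we assume an ISI standard deviation of 4.6" and applies a correlation of 0.576 from the prior study. The document gives no SD at 3 or 6 months, no correlation between baseline and those visits, and no power for Aim 3.

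**The concern.** A mean for every arm-and-visit cell includes a separate baseline mean for each arm. Randomisation makes the true baseline means equal, so those extra parameters estimate only chance differences. With complete data, the fitted cell means are the raw cell means whatever covariance structure is chosen, and the interaction contrasts are differences in raw change. Raw change fixes the coefficient on baseline at 1. Regression estimates the coefficient, and so gives the smaller variance.

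The stake is precision at 3 and 6 months. Section 1.0 lists sustained benefit among the trial's innovations, and section 2.0 makes it part of the case for yoga as a treatment option. No power is stated for this aim, so there is no documented reserve against lost precision.

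**Working it through.** **Inputs.** SD 4.6, correlation ρ = 0.576, margin 1.15, 168 evaluable per arm, one-sided 0.025 and 80% power (10.1, 10.2.1); two-sided 5% for secondary tests (10.6). Using 4.6 and 0.576 at 3 and 6 months is an assumption.

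**The plan's own figure.** With the ANCOVA variance, n per arm = 2 × (1.960 + 0.842)² × 4.6² × (1 − 0.576²) / 1.15² = 168, as stated. The change-score factor 2(1 − ρ) in place of (1 − ρ²) gives 213, and unadjusted post scores give 252. The stated sample size therefore depends on the baseline regression adjustment.

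**Standard error of a pairwise contrast at 3 or 6 months, complete data, 168 per arm.**

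| Contrast | Formula | SE |
|---|---|---|
| Change from baseline, free baseline means | 4.6 × √(2 × 2(1 − 0.576)/168) | 0.462 |
| Raw visit-mean difference, free baseline means | 4.6 × √(2/168) | 0.502 |
| Common baseline mean, or baseline covariate | 4.6 × √(2(1 − 0.576²)/168) | 0.410 |

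Generalised least squares for three arms and five visits gives the same three values. For the planned change contrast, adjustment lowers the variance by 1 − (1 − ρ²)/[2(1 − ρ)] = (1 − ρ)/2 = 21.2%, and the SE by 11.2%. The difference detectable with 80% power at two-sided 5% is 2.80 × SE: 1.29 points as planned, 1.15 adjusted. Power for a 1.3-point difference is 80.3% as planned and 88.7% adjusted.

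**Sensitivity of the variance gain against the change contrast.**

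| Scenario (assumed) | Gain |
|---|---|
| 240 per arm, 30% lost after the mid-point, post-baseline correlations 0.65 (SE 0.434 against 0.396) | 17% |
| Follow-up correlation 0.4 | 30% |
| Follow-up SD 5.0, ρ = 0.576 | 15% |
| Follow-up SD 5.5, ρ = 0.576 | 9% |
| Follow-up SD 6.0, ρ = 0.576 | 5% |
| Change from post-intervention to 6 months, compound symmetry | 0% |
| The same, with correlations decaying over time | about 4% |

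The SD rows use (s₀ − ρs₁)² / (s₀² + s₁² − 2ρs₀s₁), with s₀ = 4.6 at baseline and s₁ at follow-up. At s₁ = 5.0 this is (4.6 − 2.88)² / (21.16 + 25 − 26.496) = 2.958/19.664 = 15%.

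**The case against.** Several points on the other side stand.

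- **The planned test does use baseline.** A reader might infer that Aim 3 throws baseline away. It does not: the interaction contrasts subtract it. What is missing is the optimal weighting.
- **A 33% loss is not supported for the planned test.** That figure (1 − 0.410²/0.502²) belongs to raw visit-mean differences, which 10.7.3 plots but does not name as the test. The 21% and 33% figures describe two different contrasts and are not the ends of one range.
- **The inputs at follow-up are unknown.** Entry requires ISI of at least 10 (4.4), which restricts the range at baseline, while follow-up scores can span 0 to 28. A larger follow-up SD is plausible and shrinks the gain.
- **Maintenance may mean change from post-intervention.** On that reading there is almost nothing to gain. Section 10.7.3 does not name that contrast, however; it compares trajectories over all five visits.
- **A common baseline mean is an added assumption.** Baseline is collected after randomisation, coordinators know the assignments (5.5) and questionnaires may be completed at home (6.13). Against this, 5.5 and 6.15 withhold assignment from participants until baseline assessments are complete, and ISI is self-reported, so the assumption is reasonable.
- **Agreement with Aim 1.** A reader might expect the fix to make the post-intervention estimates of Aims 1 and 3 coincide. It need not. Aim 1 uses two separate two-group analyses, so a three-arm, five-visit model can still differ from it, particularly with missing data.

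The planned detectable difference of 1.29 is also close to the 1.3 points given at 80% power for Hypothesis 2 (10.2.2), so the aim is not crippled. None of this supplies the missing adjustment or gives a reason to omit it.

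**Conclusion.** The point holds as a matter of efficiency. Section 10.7.3 leaves the baseline means free and does not carry over the adjustment that Aim 1 uses. For the planned change-from-baseline contrasts, the avoidable variance is about 21% (11% in SE) with SD 4.6 at every visit, ρ = 0.576 at follow-up and 168 complete cases per arm. Under the other assumptions examined for those contrasts, the gain runs from about 5% to 30%.

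A reader might go further and infer bias, an inflated type I error or a threat to the primary result. The documents support none of these: the planned contrasts are valid, and Aim 1 is separate and already adjusted. The change is worth making because it uses data already collected and should not make the 3- and 6-month contrasts materially less precise.

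**What to change.** Amend 10.7.3 in one of two ways:

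1. Keep all five ISI scores as the response, but constrain the three arms to a common baseline mean: Time plus Group-by-visit terms at the four post-baseline visits, with no Group effect at baseline.
2. Model the four post-baseline ISI scores with Group, Time, Group-by-Time, Baseline ISI and Baseline ISI-by-Time.

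The first form assumes that baseline ISI is unaffected by assignment. If that is doubted, use the second, which does not impose equal baseline means and matches the adjustment in Aim 1. Keep REML and Kenward-Roger in either case.

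Also name the contrasts of interest: YOCAS against health education and CBT-I against health education, each at 3 and 6 months. This settles whether maintenance is measured from baseline or from post-intervention.

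The cost is a sentence or two in the SAP, with no extra data, visits or participants.

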#### 3.2 **Secondary Aims:**

1. To examine if YOCAS® is effective for improving objective symptoms of insomnia (sleep latency, sleep efficiency, wake after sleep onset, sleep duration, and daytime napping via actigraphy) and global sleep quality impairment (Pittsburg Sleep Quality Index) compared to CBT-I and a health education control.
2. To examine if YOCAS® and CBT-I are effective for maintaining improvements in insomnia (Insomnia Severity Index) 3 and 6 months post intervention compared to a health education control.

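### Section 10.7.3 names no 3- or 6-month contrast against health education, and its interaction test is usually significant at the plan's effect sizes even if the benefit has gone by then

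*Combined protocol and SAP*

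**What the plan says.** Section 3.2, item 2, asks whether the two active arms are effective for "maintaining improvements in insomnia (Insomnia Severity Index) 3 and 6 months post intervention compared to a health education control". Section 10.7.3, which calls this Secondary Aim 3, models the ISI total at all five visits with Time, Group and their interaction as fixed effects. It then specifies:

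- The test of group: "The impact of group on the time trajectory of insomnia will be tested via the" Time*Group interaction.
- A general rule: "Fixed effects will be tested using F tests with the Kenward-Roger degrees of freedom adjustment".
- A display: "Least-squares means for each Time and Group combination will be plotted to visualize and understand the time trajectories of insomnia".
- A further comparison: "Differences in time trajectories between the three groups will be tested with no adjustments for multiple comparisons".

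Section 10.6 adds, for the whole plan, that "95% confidence intervals will be constructed for estimation of effects". Section 10.7.1 names contrasts with confidence intervals for the primary aim, and 10.7.2 and 10.7.4 adopt its methods. Section 10.7.3 does not.

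**The concern.** The aim concerns two visits and one comparator. The interaction asks whether the arms differ in change anywhere between baseline and 6 months, so a midpoint or post-intervention difference alone can make it significant. The other F tests do not help: the Group main effect averages baseline with every later visit, and the Time effect compares no arms. The sentence on trajectories names no visit, so 3- and 6-month comparisons are neither excluded nor specified. Maintenance is not defined either: it could mean an advantage over health education at those visits, or retention of the post-intervention gain.

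At stake is a claim of durable benefit when none remains. The Introduction lists 3- and 6-month sustainability among the trial's innovations, and the Background makes sustained improvement a condition of the expected benefit to survivors. The primary comparisons are not touched.

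**Working it through.** **Inputs from the plan.** SD 4.6, correlation 0.576, 168 evaluable per arm and margin 1.15 (10.1 and 10.2.1); detectable differences of 1.3, 1.5 and 1.6 against health education (10.2.2); two-sided 5% unless otherwise stated (10.6).

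**Assumed.** Categorical Time, equal SD at all visits, complete data, both active arms equally better than control, and a midpoint benefit equal to a fraction f (0 to 1) of the post-intervention benefit. The plan gives one correlation, from its prior study, and no five-visit structure. Compound symmetry (its own example of a simplified structure) and AR(1) are therefore both shown.

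**The plan's own figure.** The adjusted SD is 4.6 × √(1 − 0.576²) = 3.760. Then n = 2 × (1.960 + 0.842)² × 3.760² / 1.15² = 167.8, so 168 per arm. At two-sided 0.025 the detectable differences are 1.26, 1.45 and 1.59, matching the stated 1.3, 1.5 and 1.6. Section 10.7.3 has no figure of its own.

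**Interaction test.** Three arms and five visits give (3 − 1) × (5 − 1) = 8 df, with a 5% chi-square critical value of 15.51. For benefit b and profile p over the four changes from baseline, the noncentrality is λ = n × (2/3) × b² × p′V⁻¹p, where V is the covariance of the changes. Under compound symmetry this becomes

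λ = 168 × (2/3) × 1.3² × q / (4.6² × 0.424) = 21.10 q, with q = Σp² − (Σp)²/5.

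The vanished profile is p = (f, 1, 0, 0); the kept profile is p = (f, 1, 1, 1).

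| f | q vanished | power, vanished | q kept | power, kept |
|---|---|---|---|---|
| 0 | 0.80 | 0.853 | 1.20 | 0.970 |
| 0.25 | 0.75 | 0.824 | 0.95 | 0.916 |
| 0.5 | 0.80 | 0.853 | 0.80 | 0.853 |
| 0.75 | 0.95 | 0.916 | 0.75 | 0.824 |
| 1 | 1.20 | 0.970 | 0.80 | 0.853 |

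A vanished profile with midpoint fraction f has exactly the same λ as a kept profile with fraction 1 − f. Over this range the test cannot tell the two apart.

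Under AR(1) with 0.576 (same f order):
- vanished: 0.868, 0.786, 0.761, 0.810, 0.898
- kept: 0.697, 0.524, 0.452, 0.507, 0.669

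Here the test is significant more often when the benefit has gone.

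**Range for the vanished case.** With 1.15 points and correlation 0.4: 0.520–0.765 (compound symmetry) and 0.458–0.627 (AR(1)). With 2.3 points: 0.99 or more throughout.

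**Other tests the text might mean.** The pairwise 4-df trajectory test of YOCAS against health education is significant in 82% of vanished cases (1.3 points, compound symmetry, midpoint effect zero or half). The Group main effect is significant in 9–24% when vanished and 49–75% when kept (compound symmetry); under AR(1) the ranges are 0.107–0.307 and 0.614–0.865.

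**Visit contrasts.** In simulation (6,000 trials per case, unstructured covariance estimated, f = 0, 0.5, 1), the baseline-adjusted 6-month YOCAS contrast was significant in about 5% of vanished and 88–89% of kept trials (AR(1): about 5% and 74%). In the vanished case, 69–80% of trials (AR(1): 62–74%) had a significant interaction while none of the four 3- and 6-month contrasts was significant.

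**Precision of a 6-month contrast (1.3 points, correlation 0.576).**
- Baseline-adjusted: SE = 3.760 × √(2/168) = 0.410, 1.3/0.410 = 3.17, power 89%.
- Unadjusted change: SE = 4.6 × √(2 × 0.424) × √(2/168) = 0.462, 1.3/0.462 = 2.81, power 80%.
- Under AR(1) the baseline-to-6-month correlation is 0.576⁴ = 0.110, and power is 74% against 49%.

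The evaluable set in 10.1 requires "actigraphy (baseline and post-intervention assessments) for primary and secondary endpoints", so 168 is not a planned number for 6 months. With an assumed further loss of 10% (151 per arm) or 20% (134 per arm) and complete cases, power at correlation 0.576 is 85% against 76%, or 81% against 71%.

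**The case against.** The best defence is that this is under-specification, not a wrong test. No sentence says that a significant interaction establishes maintenance. The opening of 10.7.3 names the visits, the active arms and the comparator. Its closing sentence presupposes several comparisons, the plotted means would show the arms converging, and the model can supply the contrasts without refitting. All of that is true, and it is why the change is cheap. But the only test named for the effect of group is the interaction, a plot is not a test, and comparisons left unspecified can be chosen after the data are seen. The confidence-interval promise in 10.6 is generic and names no 3- or 6-month ISI difference.

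The second objection is that the size depends on the effect. This stands as a qualification. For a vanished benefit of 1.0 point at correlation 0.576, the interaction is significant in 55–80% of trials (compound symmetry) or 49–65% (AR(1)); at 0.8 points, in 36–57% or 31–43%. All are far above 5%.

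Third, baseline adjustment is a matter of efficiency and its gain depends on the covariance. The loss rates are assumptions: a REML model uses all available visits, and ISI data may exceed the 168, which also requires diaries, PSQI and actigraphy. These points are accepted and do not affect the main one.

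**Conclusion.** The concern holds. As written, the stated test does not answer the aim. At 1.3 points it is significant in 76–97% of trials when the benefit is zero at 3 and 6 months, across the two covariance patterns, and it does not reliably favour a kept benefit over a vanished one. Across the plan's other effect sizes the vanished-case figure runs from 46% (1.15 points, correlation 0.4) to 99% or more (2.3 points). These figures rest on complete data for 168 per arm, equal SDs, categorical Time and the assumed correlation structures. The matter is confined to a secondary aim but should be settled before analysis.

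**What to change.** In 10.7.3:

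1. Make the tests of the aim four contrasts from the same model: YOCAS minus health education and CBT-I minus health education, each at 3 and at 6 months, each with a 95% confidence interval.
2. State that maintenance means an advantage over health education at those visits. If retention of the post-intervention difference is meant, name that contrast as well.
3. Report the Time*Group interaction as supportive.
4. Either keep the no-adjustment policy and report that four unadjusted contrasts carry a familywise error rate of roughly 16–17%, or state a multiplicity rule. At 0.0125 per contrast, baseline-adjusted power for 1.3 points at correlation 0.576 is 75%, 69% and 63% for 0%, 10% and 20% further loss; under AR(1) it is 54% with no loss.
5. For efficiency only, constrain baseline means to be equal across arms, or use baseline ISI as a covariate as in the primary model.

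The cost is SAP wording. The data and model family are unchanged.
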